5.2 Device Specification

The FUS device (H-231 FUS transducer, operating band: 0.2 MHz +/- 20% - conversion efficiency: >85% - aperture: 110.0 mm outer diameter x 44.0 mm inner diameter x 110.0 mm radius of curvature, or f/1.0- central Opening: 41.0 mm diameter; Sonic Concepts) consists of a piezoelectric crystal which converts electrical energy into mechanical energy. A function generator is used to produce sinusoidal wave forms which are applied on the transducer through a power amplifier. The RF amplifier depicts the amount of forward and reflected power (Pf and Pr) in real-time. If required, a high-impedance voltage meter will be added at the output channel of the amplifier, to directly measure the output voltage during treatment. The piezoelectric material is surrounded by a matching and backing layer, which allow lossless forward and negligible backward transmission of the ultrasound waves, respectively. The single-element spherical-segment FUS transducer has been designed to have a geometric focus, or radius of curvature, equal to 110 mm. We chose this distance to allow for targeting even in the deepest regions of the human brain. This focal distance was calculated based on numerical simulations of ultrasound wave propagation through the human skull and brain, using the k-wave MATLAB toolbox. A coupling bolus with 5 mm standoff from the exit plane will be filled with degassed water to allow ultrasound propagation into the human brain and reduce heating effects in the skull. A 44-mm central opening was introduced in the FUS transducer to facilitate therapy monitoring via a concentric and co-aligned passive cavitation detector. Microbubble acoustic

emissions will be constantly monitored during therapy. Sonication will be immediately ceased should any unwanted cavitation signals are detected. A custom purpose-built graphics user interface (GUI) will be used to control the emission and reception processes in MATLAB. We have included all the necessary functionalities in this software, enabling full control of the therapeutic process and immediate abortion in the case of an adverse effect. An isolation transformer is indeed included between the main electrical supply and the RF amplifier, which is only high-voltage device of the setup. An emergency stop button has been added in the case of an emergency that would cut off all power from the equipment.

5.3 Device Operation

The investigational device will be operated at acoustic parameters demonstrating safe and effective BBB opening in NHP followed by microbubble injection. The acoustic parameters for BBB opening are based on [name] NHP studies and correspond to an I_{SPPA} of 2.81 W/cm², I_{SPTA} of 56.3 mW/cm² and a mechanical index (MI) of 0.4. These parameters produce safe and reproducible BBB opening in NHPs. These values are well below the limits set by the FDA for ultrasound imaging applications ($I_{SPPA} < 190$ W/cm², $I_{SPTA} < 720$ mW/cm² and MI < 1.9, respectively).

The device will be operated at the same specifications as that in adults and other NHP studies since the FUS propagation will be simulated through the skull on a patient-by-patient basis based on the MRI, or CT obtained during radiation planning at the time of diagnosis (if available). CT scans will not be performed for the purposes of this research study. Extensive work has been done at [name] lab using human skull fragment and simulation, demonstrating that due to the low frequency of the FUS device (i.e., 0.25 MHz), significant skull-induced beam aberrations are not expected. In an adult skull, the focal shift is on the order of a few mm. Therefore, we expect a lower shift through the thinner skull of pediatric patients. The acoustic field will be simulated based on the CT of each patient, if available. Otherwise we will use the MRI scan to acquire structural information about the skull geometry. The 3D simulation will be performed using the kWave toolbox in Matlab. The simulation will be conducted first in free-field (i.e., only water) and then using the CT/MRI scan of the patient, to calculate the attenuation coefficient at a defined beam trajectory and transducer location. No assumptions regarding bone properties are required (if a CT scan is available), since the speed of sound is directly derived from the Hounsfield units of the CT scan. If a CT is not available, we will use the skull contour from the MRI and assume a bone density of 1.35 g/cm³ (this is the average skull density in pediatric patients [47]). We will perform a total of at least 10 simulations, by allowing a margin of +/- 2mm Euclidian error and +/- 20° angular error. The attenuation coefficient and derated pressure will be calculated as average values across all the simulations. The device will not need maintenance but will be calibrated once every 6 months using a hydrophone. Please see device specifications attached in appendix 7.0.

5.4 Potential Risks

Ultrasound and MRI are generally considered safe imaging modalities. However, there are potential risks related to their usage.

Potential adverse events related to the use of FUS include hemorrhage, and worsening edema. In all human studies, however, no DLTs were observed and there has been no added toxicity due to opening of the BBB through the FUS. Although Zhu et al. [48] has shown that FUS allows evaluation of circulating free DNA raising concerns for tumor dissemination, there has been no preclinical or clinical evidence of increasing the risk for development of metastases in these subjects. We will evaluate and report in the current study whether there has been any rapid development of metastatic disease.

Although ultrasound exposure at high intensities may produce unintended biological effects in the body, such as hemorrhage and edema, our study will be limited to intensities far below the FDA-approved limits for imaging applications ($I_{SPPA} < 190 \text{ W/cm}^2$, $I_{SPTA} < 720 \text{ mW/cm}^2$ and MI < 0.8). FUS is expected to induce some intended mechanical effects in the brain, but there has been no damage reported in the literature during low-intensity sonication. Sonications at relatively high acoustic pressures have resulted in moderate hemorrhage at the targeted region leading to instances of edema and inflammatory response. We will therefore operate close to the threshold for stimulation to avoid any unwanted effects and minimize the risk for the subject. It is possible that the subject will feel some heat from the ultrasound propagation through the skull. We will account for potential heating by using a cooling medium (i.e., cold water) between the transducer and the skull. All the necessary hardware and software precautions will be taken, in order to eliminate the possibility of transducer malfunction or protocol breach during the clinical sessions.

5.5 Prior and Concomitant Therapy

Although BBB opening is reversible and transient, it may lead to unintended diffusion of pharmaceutical molecules into the brain parenchyma. To avoid such potential effects, medication withholding will be judged based on the subject's diagnosis, condition, and medication type. Examples of medications that will not be withheld include are anti-convulsants steroids and anti-emetics. In all clinical human studies so far despite the use of supportive care and anesthesia no serious adverse events were reported.

5.6 Packaging

The ultrasound transducer and the associated electrical components, i.e. function generator, power amplifier, and hydrophone, will be gathered in a mobile cart. All components will be connected prior to the subject's arrival and will be checked by two investigators to ensure smooth operation and safety.

The neuronavigation system along with the accompanying equipment, i.e. infrared camera, reflecting beads, holders, and other ancillary components, will be packed separately and gathered in a mobile cart. The parts will be assembled following the subject's arrival and the imaging beads will be attached to the subject's head and the transducer to allow for real-time neuronavigation.

5.7 Receiving, Storage, Dispensing and Return

5.7.1 Receipt of Study Device

The device will be delivered to the operating room from the storage room in the investigative site by the researchers prior to the procedure.

5.7.2 Storage

The ultrasound system will be stored in a room equipped with a locker and will be kept under room temperature until usage.

The neuronavigator system will be stored in the same locked room with the ultrasound system, and will also be kept in room temperature until usage.

DEFINITY® microbubble vials will be stored in the Research Pharmacy in a hospital grade refrigerator under 4 °C until usage. DEFINITY® microbubbles will be removed from refrigerator before the subject's arrival, to allow them to acquire room temperature.

5.7.3 Dispensing of Study Device Agents

The research pharmacy will dispense the DEFINITY® microbubbles and MRI/PET contrast agent. The radiation oncologist on the study will be performing the procedures to the subject, and the other researchers will deliver the ultrasound device from the storage room to the procedure room.

5.7.4 Return or Destruction of Study Device

The device should be returned to the following address if damaged: [name].

6. STUDY OBJECTIVES

6.1 Primary Objective

The primary objective of this study is to evaluate the feasibility of safely opening the BBB in children with progressive DMG treated with oral Panobinostat using FUS with DEFINITY® microbubbles and neuro-navigator-controlled sonication.

With the current study we are planning to evaluate the safety and feasibility of using FUS and open-space neuronavigator-controlled sonication to open one, two or three tumor sites. For the purpose of the study we will be administering oral Panobinostat in children with progressive DMG. This drug has a known toxicity profile, dose and well documented efficacy against many metastatic cancers. Successful opening and closing of the BBB will be confirmed with periodic MRIs.

Safety will be assessed by evaluation of physical and neurologic examinations, laboratory studies, radiographic studies, and by adverse events as per the CTCAE version 5.0. An adverse event is

any new or worsening symptom or clinical finding which occurs during the study period. Adverse events are to be recorded irrespective of causality on the adverse event form. Each event will be described by its severity (mild, moderate, severe, life-threatening), duration, and relation to the study medication (unrelated, unlikely, possible, probable, and definite).

6.2 Secondary Objective

- To evaluate the 6-month Progression Free Survival (PFS6) and 6-month Overall Survival (OS6)
- To determine blood brain barrier/tumor imaging changes using FUS in children with progressive DMG

7. STUDY DESIGN

7.1 General Design

The purpose of this study is to evaluate the feasibility of opening the BBB safely using specific parameters of focused ultrasound in progressive/recurrent diffuse midline gliomas in one, two or three tumor sites and receive Oral Panobinostat 15 mg/m². The study will consist of a minimum of 3 to a maximum of 15 subjects. See [section 7.3](#) for a treatment schema.

The clinical neuronavigator will be identical to the NHP study with the difference of human module in the software used, as well as employing a separate set of navigation tools that are used for human subjects only.

7.1.1 Subject Recruitment

Subjects of all races and ethnic groups are eligible for this trial.

Subjects will be recruited from the Pediatric Oncology and Pediatric Neurosurgery practices/clinics at Columbia University Irving Medical Center (CUIMC).

7.1.2 Registration Procedures

CUIMC research participant registration

Confirm eligibility as defined in the section entitled Criteria for Subject Eligibility.

Obtain informed consent, by following procedures defined in section entitled Informed Consent Procedures, along with applicable institutional policies and federal regulations.

Only Investigators/Research Personnel properly trained and delegated to consent subjects for this protocol will participate in the consenting process. Furthermore, properly delegated Physician Investigators (e.g., MD, MD-PhD) are required to sign/verify a protocol specific Eligibility Checklist for each subject enrolled on the study, in addition to providing the relevant source documentation confirming subject eligibility.

7.2 Trial Design

The trial will follow a 3+3 “NOTS” or Number of Tumor Sites escalation scheme. The “number of tumor sites” in reference to here in the number of openings in the blood brain barrier using Focused Ultrasound (FUS). Subjects will start the first cycle of the treatment arm with 1 tumor site and move on to incrementing NOTS levels as depicted in Figure 3, if no dose limiting toxicities

(DLTs) are observed (we use the term Dose Limiting Toxicity where dose = Number of Tumor Sites (NOTS)):

- 1 tumor site (level "NOTS Level A"),
- 2 tumor sites (level "NOTS Level B") or
- 3 tumor sites (level "NOTS Level C")

For a detailed description of DLTs please refer to [Section 12.2](#).

[figure not shown]

Figure 3: NOTS (Number of tumor Sites) Escalation Schema

For each subject the following FUS NOTS escalation scheme will be followed:

- Each subject will start off with receiving FUS treatment in 1 tumor site (NOTS Level A) for Cycles 1 and 2.
- If 0 DLTs are noted during pre-cycle 3 follow-ups and MRI (without contrast), the subject will receive FUS treatment at 2 tumor sites (NOTS Level B) in the 3rd cycle.
 - If 1 DLT is noted during pre-cycle 3 follow-ups and MRI (without contrast), the subject will discontinue treatments and will come off the study (please refer to [Section 12.3](#) for Early Stopping Guidelines). Other subjects may continue to enroll.
 - If 2 DLTs are noted at the same NOTS level, enrollment will be halted following Early Stopping Guidelines detailed in [Section 12.3](#).
- If 0 DLTs are noted during pre-cycle 4 MRI (without contrast) and follow-up, the subject will continue to receive FUS treatment at 2 tumor sites (NOTS Level B) in the 4th cycle.
 - If 1 DLT is noted during pre-cycle 4 follow-ups and MRI (without contrast), the subject will discontinue treatments and will come off the study (please refer to [Section 12.3](#) for Early Stopping Guidelines).

refer to [section 12.3](#) for Early Stopping Guidelines). Other subjects may continue to enroll.

- If 2 DLTs are noted at the same NOTS level, enrollment will be halted following Early Stopping Guidelines detailed in [Section 12.3](#).
- If 0 DLTs are noted during pre-cycle 5 MRI (without contrast) and follow-up, the subject will receive the next escalated FUS treatment at 3 tumor sites (NOTS Level C) in the 5th cycle.
 - If 1 DLT is noted during pre-cycle 5 follow-ups and MRI (without contrast), the subject will discontinue treatments and will come off the study (please refer to [section 12.3](#) for Early Stopping Guidelines). Other subjects may continue to enroll.
 - If 2 DLTs are noted at the same NOTS level, enrollment will be halted following Early Stopping Guidelines detailed in [Section 12.3](#).
- If 0 DLTs are noted during pre-cycle 6 MRI (without contrast) and follow-up, the subject will continue to receive FUS treatment at 3 tumor sites (NOTS Level C) in the 6th cycle.
 - If 1 DLT is noted during pre-cycle 6 follow-ups and MRI (without contrast), the subject will discontinue treatments and will come off the study (please refer to [section 12.3](#) for Early Stopping Guidelines). Other subjects may continue to enroll.
 - If 2 DLTs are noted at the same NOTS level, enrollment will be halted following Early Stopping Guidelines detailed in [Section 12.3](#).

Within each cycle, if 1 DLT is noted the subject will discontinue treatments and will come off the study (please refer to [section 12.3](#) for Early Stopping Guidelines). Other subjects may continue to enroll.

If 2 DLTs are noted at the same NOTS level for a subject, study enrollment will be halted following Early Stopping Guidelines detailed in [Section 12.3](#).

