12. DOSE MODIFICATION AND WITHDRAWAL CRITERIA

12.1 Dose modification

Doses of the drug (Panobinostat) will not be reduced. Instead, if the patient recovers from any previous adverse event (AE) or Serious Adverse Event (SAE) and the principal investigator determines that it is in the patient's best interest to proceed with the study therapy for maximal therapeutic benefit, the next scheduled FUS/treatment should be administered. During any cycle, if grade 2 or higher toxicity is unresolved before the next scheduled FUS treatment, treatment will be halted and will be re-evaluated upon resolution of toxicity. The treatment may be resumed for the subject if the toxicity is resolving before the subsequent scheduled FUS treatment.

If the treatment related toxicity experienced toxicity (Grade 2 or higher) persists for more than 21 days or there is ≥ 1 Dose Limiting Toxicity (DLT), the subject will not have the subsequent FUS. If two DLTs occur at the same NOTS level, further enrollment will be halted.

Additional modifications to timing of doses may be performed at the discretion of the PI.

General guidelines: Patients with minor signs of increased intracranial pressure may be managed by steroids and mannitol. If patients develop significant new neurologic deficits or a change in level of consciousness (Grade 2 or higher symptomatic intracranial hemorrhage or stroke), the treatment will be stopped.

Criteria to proceed to subsequent FUS/treatment include :

- Absence of intercurrent active infection or intercurrent illness
- Resolving treatment related toxicity experienced in prior FUS /treatment to grade 2 or less
- Patient decides to withdraw

Within each cycle, if 1 DLT (defined in [Section 12.2](#)) is noted the subject will discontinue treatments and will come off the study (please refer to [section 12.3](#) for Early Stopping Guidelines). Other subjects may continue to enroll.

If 2 DLTs are noted at the same NOTS (Number of Tumor Sites) level for a subject, study enrollment will be halted following Early Stopping Guidelines detailed in [Section 12.3](#).

Subjects as well as their family members will be educated about signs and symptoms of increased intracranial pressure and neurological deficit, for which the study investigators should be notified, and emergent medical attention should be sought.

This protocol will be uniform for all subjects enrolled in the trial.

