12.2 Dose Limiting Toxicities

Dose limiting toxicities (DLT) will be defined as any new (or increased from baseline), treatment related (drug and/or device):

1. Neurological deficits based on neurological examination which are grade 3 or greater nervous system adverse events at least possibly attributed to sonication (as defined by CTCAE v5.0).

2. Grade 2 or higher symptomatic intracranial hemorrhage or stroke.

These deficits include but are not limited to changes in level of consciousness, new onset speech difficulties (aphasia, mutism, dysarthria), confusion, visual field deficits, focal weakness, seizures. The DLT period is defined as starting the day of the first scheduled FUS treatment and lasting until 14 days after the last scheduled FUS treatment.

Furthermore, DLT criteria include any systemic treatment- related Grade 3 or higher hematologic or non-hematologic toxicity within a period of 14 days after the scheduled FUS treatment. Examples of exceptions could include:

- I. Grade 3 thrombocytopenia without bleeding, Grade 3 or 4 lymphopenia, Grade 3 neutropenia without fever.
- II. Nausea, vomiting or diarrhea responding to medical management within 48 hours
- III. Electrolyte disturbances that are asymptomatic and response to supportive care within 48 hours; hyperglycemia \leq 12 hours

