12.3 Early Stopping Guidelines

In the event 2 DLTs occur for more than 1 subject at a NOTS (number of tumor sites) level (as defined in [section 7.2](#)), study enrollment will be immediately halted. There will be at least 14 days following completion of the FUS treatment of the patient(s) on study before any subsequent patient is enrolled. After re-evaluation and consultation with the HICCC DSMC board, the trial may re-initiate enrollment with adjusted treatment parameters after a consensus is agreed upon by the Sponsor-Investigator and the HICCC DSMC, and a subsequent modification is reviewed/approved by the local PRMC/IRB. If a consensus cannot be reached, no further enrollment will be permitted on the trial and closure procedures will be initiated. In addition, the study will be discontinued at any given time if more than 20% of patients experiencing medical complications including the development of significant, irreversible deterioration during the treatment. With this rule and under the assumption of the true probability of having the medical complication is 10%, the probability of stopping the study due to the medical complication is 0.02 when the targeted total sample size is 6 and is 0.053 when the targeted total sample size is 9.

If the MRI to confirm opening of the BBB for any subject is irregular at any time during the cycles, the subject will not receive the scheduled dose treatment until a decision is made by the investigating team.

If the MRI confirm the closure of the BBB for any subject are irregular at any time, the subject will not receive any further FUS treatments and will receive another MRI to confirm closure every 48 hours for a maximum of 3 times. If the subject does not show BBB closure after 3 MRIs, the subject will come off the study. The subject will be able to receive the scheduled dose of drug, unless otherwise specified by the investigating team.

Response and progression will be evaluated in this study using the international criteria proposed by the updated Pediatric Response Assessment in Neuro-oncology (RANO) guidelines[49].

| Criterion | Complete Response | Partial Response | Stable Disease | Progressive Disease |
|----------------------------------------|---------------------|---------------------|---------------------------------|---------------------|
| T1-weighted post-Gd measurable disease | None | ≥50% decrease | <50% decrease but <25% increase | ≥25% increase |

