12.4 Early Withdrawal of Subjects

- If the subject fails to comply with the defined treatment plan and follow-up evaluations, the subject may be removed from the study at the discretion of the treatment investigator
- If the subject withdraws consent for continued participation, he/she will be removed from the study
- If the subject develops significant, new neurologic deficits or a change in level of consciousness a CT or MR scan may be performed to evaluate for hemorrhage/edema. If symptoms remain unmanageable by medications, craniotomy may be performed for resection of tumor, necrosis, or hemorrhage if medically indicated
- The reason for study removal and the date the subject was removed should be documented in the Case Report Form (CRF)
- If the treatment related toxicity experienced toxicity (Grade 2 or higher) persists for more than 21 days or ≥1 Dose Limiting Toxicity, the subject will not have the subsequent FUS and early withdrawal will be considered.

The primary endpoint of this study is safety. As such, subjects will be withdrawn from the study as per the guidelines outlined above. Should similar toxicities occur in more than one subject; early interruption of the study will be considered.

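### The 2-DLT enrollment halt is stated eight times in three wordings that disagree, and no text says which one governs

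*Combined protocol and SAP*

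**What the plan says.** Section 7.2 labels the design 3+3, with the number of sites opened (NOTS Level A, B or C) in the place of dose. The enrollment halt then appears in three forms.

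- **No subject named (five statements).** Each of the four pre-cycle checks in 7.2 (cycles 3, 4, 5 and 6) has a bullet reading "If 2 DLTs are noted at the same NOTS level, enrollment will be halted following Early Stopping Guidelines". Section 12.1 has "If two DLTs occur at the same NOTS level, further enrollment will be halted", without a cross-reference.
- **One subject (two statements).** Section 7.2 ends with "If 2 DLTs are noted at the same NOTS level for a subject, study enrollment will be halted". Section 12.1 repeats it: "If 2 DLTs are noted at the same NOTS (Number of Tumor Sites) level for a subject, study enrollment will be halted". Both refer to 12.3.
- **More than one subject (one statement).** Section 12.3 has "In the event 2 DLTs occur for more than 1 subject at a NOTS (number of tumor sites) level", after which enrollment stops at once and may reopen only after agreement with the DSMC and PRMC/IRB approval of a modification.

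For the individual child, 7.2 says "Within each cycle, if 1 DLT is noted the subject will discontinue treatments and will come off the study", while others may still be enrolled. Section 12.2 runs the DLT period from the first scheduled FUS, "lasting until 14 days after the last scheduled FUS treatment". Section 12.4, covering both a DLT and a prolonged Grade 2 or higher toxicity, says "the subject will not have the subsequent FUS and early withdrawal will be considered".

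Separately, after an allergic or other reaction to therapy, 13.2 withdraws the subject. A nearly identical sentence in 13.3 discontinues the study.

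**The concern.** Section 12.4 names safety as the primary endpoint, and this trigger protects the next child to be enrolled. The three wordings attach it to different events: a count of DLTs at a level, a count within one child, and a count involving more than one child. Section 12.1 contains two of the three. Someone working from a single sentence could reach a different decision from a colleague working from another, and departmental QA, which reports stopping rules to the DSMC under 13.4, has no single rule to report against.

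**Working it through.** The plan gives no operating characteristic for the 2-DLT trigger, so there is no figure to reproduce. The stopping probabilities in 12.3 belong to the separate rule on medical complications in more than 20% of patients. The check is a count of statements and a comparison of what each requires.

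**1. Count.** 7.2 bullets 4 + end of 7.2 1 + 12.1 2 + 12.3 1 = 8. By wording: 5 unqualified + 2 one-subject + 1 more-than-one-subject = 8. Of the seven outside 12.3, the four bullets and the two one-subject sentences (4 + 2 = 6) refer to 12.3. The unqualified sentence in 12.1 does not.

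**2. Action by DLT pattern at one NOTS level.** Section 12.3 is read in its natural sense: two or more DLTs in total, involving more than one child.

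| Pattern | Unqualified (total at least 2) | One subject (some child has at least 2) | 12.3 (total at least 2, more than one child) |
|---|---|---|---|
| A: two children, one DLT each | halt | no halt | halt |
| B: one child, two DLTs | halt | halt | no halt |
| C: one child with two, another with one | halt | halt | halt |
| D: two children, two each | halt | halt | halt |

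The wordings part company in A and B and agree in C and D. Taken together as sufficient triggers, they halt in all four.

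**3. Can the one-subject wording ever be met?** The child leaves at the first DLT, but the 12.2 window stays open for 14 days after the last scheduled FUS. DLTs also include neurological deficits, hemorrhage or stroke, and systemic toxicity. A second DLT can therefore be found with or after the first, and the sentence is not empty. However, 12.2 lists deficits that can occur together (altered consciousness, speech difficulty, focal weakness), and no text says whether one episode with several of them is one DLT or two.

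**4. Which wording governs?** The six references to 12.3 can be read as adopting its trigger, or only as pointing to its procedure for the halt (waiting period, DSMC consultation, PRMC/IRB review). The text does not decide. The 7.2 bullets also stand under a lead-in that describes the scheme for each subject, so even they could be read per child.

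**5. Secondary mismatches.** After one DLT, 7.2 takes the child off study, while 12.4 only considers withdrawal; FUS stops under both. On reactions, 13.2 acts on the subject and 13.3 on the study.

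**The case against.** The strongest reply is that any one trigger suffices. No statement says that enrollment halts only if its own condition is met, so a narrower sentence does not cancel a broader one. The unqualified sentence in 12.1 halts in all four patterns and does not refer to 12.3. The 3+3 label and the natural reading of 12.3 also support counting across children. All of this stands.

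Two stronger readings are tempting, and the documents support neither. A reader might infer that the trial would go on enrolling after two children each had a DLT at a level. That requires applying one of the two one-subject sentences and disregarding the rest. A reader might also take 12.3 to require two DLTs in each of two children. The grammar allows it, but it is strained in a scheme where a child leaves at the first DLT.

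Other provisions limit the practical harm. Section 12.4 says early interruption will be considered if similar toxicities occur in more than one subject. Section 12.6 ends the investigation after a single procedure-related death, life-threatening event or other serious adverse event. The DSMC meets twice a month (13.3), and 11.3.4 sets 24-hour reporting to it of serious adverse events that are not unanticipated problems. These reduce the consequence without settling the trigger. The 12.4 provision is discretionary, 12.6 is confined to events due to the procedure whereas DLTs include drug-related systemic toxicity, and DSMC review is not a definition of the rule.

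**Conclusion.** The contradiction is real and is worth correcting in the next amendment. Eight statements in three wordings disagree on two of the four patterns set out above: one DLT in each of two children, and two DLTs in one child. Nothing in the text ranks them. The most natural reading of the whole does halt enrollment in the first of these cases, so this is an inconsistent safety rule with limited practical harm, not a missing one.

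No probability is attached. The protocol gives no DLT rate, and an assumed one would show how often DLTs cluster, not how often the wording would mislead. The conclusion rests on the text alone. The escalation schema (Figure 3) is not available in the copy reviewed and might show the intended count.

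**What to change.** Use one sentence in 7.2, 12.1 and 12.3, for example: *If 2 or more DLTs occur at the same NOTS level, counted across all subjects, enrollment is halted immediately and the procedure in 12.3 is followed.* Delete the qualifiers *for a subject* and *for more than 1 subject*.

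In 12.3, add two clarifications:

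- Two DLTs in one subject count as two only if they are distinct events. Several deficits from one clinical episode count as one DLT. This keeps the existing one-subject halt without letting a single event trigger it. The investigators should confirm that they want that halt, since the present 12.3 points the other way.
- Section 12.6 applies in addition to the DLT rule.

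Secondary harmonization: 12.4 should say that a subject with a DLT comes off study, as in 7.2, and keep discretion only for toxicities that are not DLTs. Section 13.3 should follow 13.2 and withdraw the subject, with termination of the study governed by 12.6.

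The cost is wording in five sections (7.2, 12.1, 12.3, 12.4, 13.3), with no added patients, visits or procedures. The small downside is that a non-serious reaction, which 13.3 now says stops the whole study, would no longer do so.
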